- Retention (the proportion of patients that enrol into the study who complete follow-up measurements)
- Safety (the incidence and severity of adverse events)
- Acceptability (Likert scale and open-ended survey questions, posts in community forum)

The secondary aim is to assess the preliminary efficacy of PreActiv's digital prehabilitation by measuring pre- to post-intervention changes to:

- Cardiorespiratory fitness ($VO_{2\text{PEAK}}$, ventilatory threshold)
- Functional fitness (1-minute sit-to-stand test, 1-minute seated push-up test)
- Resting blood pressure and heart rate
- Self-reported physical activity level (International Physical Activity Questionnaire Short Form)
- Quality of life (EuroQoL EQ-5D-5L Scale)
- Mood (Hospital Anxiety and Depression Scale)

An exploratory aim is to evaluate the economic/environmental impact of PreActiv's digital prehabilitation:

- Cost per patient to deliver PreActiv's digital prehabilitation, with comparison to published costs for face-to-face and telemedicine prehabilitation programmes

- Environmental impact avoided by performing prehabilitation at home via PreActiv's digital prehabilitation compared to the estimated hypothetical emissions associated with participants travelling to the hospital three times per week for six weeks for face-to-face prehabilitation.

3. Study design

A single-arm pilot study conducted at the Royal United Hospitals Bath NHS Foundation Trust (RUH). All participants will be allocated to receive PreActiv's digital prehabilitation alongside usual care. Usual care at the RUH involves a digital preoperative assessment of surgical risk and relevant investigations such as electrocardiogram (ECG) and blood tests for all patients. For some patients, usual care may also include seeing an anaesthetist (depending on their risk factors) and seeing other allied healthcare professionals, e.g., dietician (depending on their individual requirements or the nature of the surgery). Prehabilitation is not standard of care at the RUH. Pre-intervention testing will be conducted in week 0 and post-intervention testing will be conducted in week 7.

4. Participant eligibility

The following inclusion criteria will define patients eligible for the study:

- Planned for major elective surgery ≥ 10 weeks from time of recruitment

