- **Compliance:** If participants report an RPE <5 for aerobic and/or resistance exercise on two occasions, they will be telephoned by a researcher to assess why they have scored their RPE <5. If poor technique or lack of understanding is causing RPE <5, education on the importance of intensity and how to achieve higher intensities will be provided. If technique/understanding are not the issue, and the programme is too easy, the course would be adapted manually (in the future, the adaptation of the course would be partially automated).

Non-exercise intervention

General advice and information on services relating to alcohol consumption, smoking, and nutrition will be provided in the PreActiv eBook. Specific instruction or advice on alcohol, smoking, and nutrition is beyond the scope of this iteration of the PreActiv digital platform but will be included in subsequent versions.

A community forum will be provided within the PreActiv digital platform, which will allow people undergoing similar surgeries to share experiences, discuss queries, and seek support from peers. Participants will have access to the community forum throughout their prehabilitation programme, and for one month post-surgery, to allow participants to share comments about their surgery and recovery experience. All comments made in the community forum will be archived for later analysis in order to further refine and evaluate PreActiv's digital prehabilitation.

There will be a check-in session on a Monday with a member of the research team via the community forum so users can access health professional support. This support is included in the implementation plan and is part of the intervention.

d. Measurements

Primary outcome measurements will be collected throughout the study (week 0-7).

Feasibility

- Recruitment rate: the proportion of patients invited that provide written informed consent
- Uptake: the proportion of patients invited that are willing to be screened for eligibility
- Screen-pass rate: the proportion of willing patients that pass screening for eligibility
- Adherence: the proportion of exercise sessions offered that are attended, assessed based on the number of sessions completed on the PreActiv platform (note: subsequent exercise sessions only become available to participants once they have watched the previous video).
- Compliance: the proportion of exercise sessions that are completed as prescribed:

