 - Exercise intensity: comparing the RPE reported by participants to the target RPE prescribed (i.e., RPE 5-10/10 is the target, so RPE 6/10 would be compliant but RPE 4/10 would be non-compliant). The proportion of aerobic and resistance sessions that are completed at the target intensity will be reported. It has been shown that an RPE score reported at the end of an exercise session is equivalent to the average RPE reported after each exercise (Day et al., 2004).

- Exercise type: after each session, participants will respond to the question: “how much of the session could you complete?” with options: all / most / some / none. If they select any option other than “all”, they will be asked to identify any exercises included in their session that they couldn’t complete from a list. Any sessions where ≥ 1 exercise was not completed will be deemed non-compliant to the type of exercise prescribed. The proportion of sessions where all exercises are completed will be reported.
- Duration: after each session, participants will respond to the question: “how much of the session could you complete?” with options: all / most / some / none. If they select any option other than “all”, they will be asked to identify any exercises included in their session that they couldn’t complete from a list. If they do not select any specific exercise, then we infer that participants were unable to perform the exercises for the required duration. Any sessions where most / some / none is reported with no specific exercise identified will be deemed non-compliant to duration. The proportion of sessions where exercises were performed for the target duration will be reported.
- Retention: the proportion of patients that enrol into the study who complete follow-up measurements
- Safety: the incidence and severity of adverse events reported during the weekly check-in session with a member of the research team, and via a free-text response box after each exercise session to be completed if the participant indicates that they could not perform all exercises.

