 - 1-minute testing protocols have been selected to increase the emphasis on measuring endurance rather than muscular strength, due to the associations between cardiorespiratory fitness and surgical outcomes. The 1-minute sit-to-stand test has been shown to induce similar cardiorespiratory responses as cardiopulmonary exercise testing in COPD patients (Gephine et al., 2020), and has been implemented in prehabilitation trials (Bradley et al., 2023). The 1-minute seated push-up test is a relatively novel assessment, and has been shown to correlate with other functional fitness measures (Chokphukiao et al., 2023, Poncumphak et al., 2023).
- Self-report physical activity: Participants will complete the IPAQ short-form questionnaire to self-report days per week and minutes per day of vigorous intensity physical activity, moderate intensity physical activity, walking, and sitting. 'MET-hours' (MET = metabolic equivalent of task) per week will be calculated. This information will be compared to the WHO guidelines on physical activity and sedentary behaviour.

Psychological assessments

- Quality of life: Participants will complete the EQ-5D-5L to provide insights into mobility, self-care, usual activities, pain/discomfort, and anxiety/depression.
- Mood: Participants will complete the Hospital Anxiety and Depression Score

Economic & environmental

- Cost per patient to deliver PreActiv's digital prehabilitation, with comparison to published costs for face-to-face and telemedicine prehabilitation programmes
- Environmental impact avoided by performing prehabilitation at home via PreActiv's digital prehabilitation compared to the estimated hypothetical emissions associated with participants travelling to the hospital three times per week for six weeks for face-to-face prehabilitation. Publicly-available carbon emissions data will be used for calculations.

e. Data analyses

The primary aim of this study is to test feasibility of the PreActiv's digital prehabilitation. Feasibility will be assessed by reporting proportions and comparing to predefined progression criteria (for adherence and retention). This pilot study is not adequately-powered to investigate the statistical significance of pre- to post-intervention changes to secondary outcome measures. As such, data analyses will be predominantly descriptive. Effect sizes will be reported to convey the magnitude of pre- to post-intervention changes to secondary outcomes.

6. Patient and public involvement (PPI)

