Risks of exercising: While exercise training provides long-term benefits that reduce the risk of adverse health events, the risk of acute injury and medical events is elevated whilst exercise is being performed. In particular, our exercise intervention is to be performed at vigorous to maximal exertion (i.e., a rating of perceived exertion 5-10/10), which increases the risk of adverse reactions if not appropriately prescribed. To mitigate these risks, all participants will be thoroughly screened for exercise contraindications as per in the inclusion/exclusion criteria, and people presenting with contraindications will be excluded from the study on safety grounds. Furthermore, the exercise prescription has been developed by physicians, physiotherapists, and clinical exercise physiologists, meaning the exercises that have been selected are deemed suitable for the population by a multidisciplinary team of experts. In addition, the exercise programme is tailored to the participants mobility and fitness level. The exercise videos embedded in the platform provide visual and verbal instructions for correct technique to reduce the risk of injury. Participants are also advised to separate their sessions with rest days to allow for recovery. As the risk of acute injury and medical events can be minimised, but not eliminated, participants will be provided with instructions for setting up a safe exercise space at home, and will be advised to stop exercising upon the onset of red-flag symptoms (e.g., pain, dizziness, light-headedness, feeling generally unwell) and to seek medical attention. Furthermore, there will be access to first aid and immediate life support (including defibrillator) during cardiopulmonary exercise testing.

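### The post-session adverse-event box opens only when a session was not fully completed, so events that limit no exercise rest on a forum check-in with no stated adverse-event question

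*Combined protocol and SAP*

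**What the plan says.** The protocol summary and section 2 list safety, defined by how often adverse events occur and how severe they are, among the primary outcomes. Section 5d sets the collection window for primary outcomes at weeks 0 to 7. Under Safety it names two sources: the weekly check-in with research staff, and reports made "via a free-text response box after each exercise session to be completed if the participant indicates that they could not perform all exercises".

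The form shown after each session asks how much of it could be done (all, most, some or none). That answer feeds the compliance outcome: "The proportion of sessions where all exercises are completed will be reported". The form as described does not ask about symptoms.

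The only check-in described is in section 5c (Non-exercise intervention), a Monday session "with a member of the research team via the community forum so users can access health professional support". The forum is a shared space, "which will allow people undergoing similar surgeries to share experiences, discuss queries, and seek support from peers", and its comments are archived for analysis. Neither section gives an adverse-event question for the check-in.

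Two other contacts appear in section 5c (Monitoring of exercise intervention). Four days without a session leads to an email and then, after two days without a reply, a telephone call. RPE below 5 on two occasions also leads to a call. Neither is named as a safety source. Section 8 says participants "will be advised to stop exercising upon the onset of red-flag symptoms" and to seek medical attention. On analysis, section 5e says "Feasibility will be assessed by reporting proportions and comparing to predefined progression criteria (for adherence and retention".

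**The concern.** The box asks about events only when the participant has already reported falling short. Whether an exercise was finished and whether an adverse event occurred are different questions. Someone can finish every exercise and have pain that evening, or have a symptom during a session and carry on. Events of that kind fall to the check-in, where the text describes an offer of support and does not say that each participant is asked about events.

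The pilot is meant to inform a larger study of vigorous exercise done at home, which section 8 acknowledges carries a raised risk of acute injury and medical events while it is being performed. If few events are recorded, a reader needs to know whether few occurred or whether the question was put only in some circumstances. The completion filter makes that harder to judge for a primary outcome.

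**Working it through.** The plan gives no figure for this point, so the check sets the rules side by side.

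**Step 1: when the box opens.** Sections 5d (Compliance) and 5d (Safety) together imply that any answer other than 'all' opens it. The session need not have been abandoned; one exercise left out or cut short is enough.

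**Step 2: which events reach which named source.**

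| Event | Opens the box? | Named sources |
|---|---|---|
| Red-flag symptom that stops the session | Yes, if the form is then answered | Box and check-in |
| Symptom that makes the participant omit or shorten one exercise | Yes | Box and check-in |
| Later injury that limits an exercise in the next attended session | Yes, at that session | Box and check-in |
| Symptom in a session answered 'all' that does not limit the next one | No | Check-in only |
| Delayed or between-session event that resolves before the next session | No | Check-in only |
| Event after the last session | No | Check-in only; the text does not say how long check-ins run |
| Event that stops the participant starting any further session | No, as no form follows | Check-in only; the adherence call may reveal it |

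The gap is the last four rows.

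**Step 3: whether another stated route covers those rows.**
- The adherence call could bring out the last row, and the RPE call could bring out a symptom that led someone to ease off. Both depend on a trigger and neither is named as a source of adverse events.
- Section 8 directs participants to medical attention and does not mention telling the study team.
- The Appendix 2 survey has no symptom item, and section 5d makes its answers unattributable to a participant.
- The week-7 visit lies inside the collection window, but the Safety entry does not name it as a source.

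**Step 4: size.** Let s be the share of events that never open the box and c the share of those raised at the check-in. The share missed through the named sources is s × (1 − c). The documents give neither input. Under assumed values:
- s = 0.25, c = 0.9: 0.25 × 0.1 = 2.5%
- s = 0.50, c = 0.5: 0.50 × 0.5 = 25%
- s = 0.75, c = 0: 0.75 × 1 = 75%

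This range shows only that the answer depends wholly on unknown inputs. It is not an estimate.

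**Step 5: effect on the decision.** The sample-size argument in section 5a and the progression table use adherence and retention. Safety enters neither, so N = 34 and the stop/amend/go rule stand whatever is recorded here.

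**The case against.** The strongest reply is that the plan catches the events that matter most. The trigger is low: a symptom that spoils a single exercise opens the box, and an injury that carries over opens it at the next attended session. A participant who stops exercising altogether should be emailed and then, if there is no reply, telephoned. Section 5d names the check-in as a source of adverse events, so staff may well ask there, and a script may sit in a working document. Exercise tests are monitored directly by staff. Asking after every session would also collect background complaints that a single-arm study cannot attribute.

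Most of this stands, and it rules out some stronger readings. A reader might infer that every symptom that did not stop a session is lost to the box; the 'other than all' trigger contradicts that. A reader might infer that nobody is asked about events at the check-in, or that the number asked can never be established. The documents support neither: the absence of stated wording does not show that nobody asks, and archived forum comments might allow prompts and replies to be counted afterwards.

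The reply does not meet the remaining gap. For events that limit no exercise, and for those after the last session, the check-in is the only named source, and the text gives it no question. The telephone calls are not designed to find such events. The background-symptom objection is a real cost of asking, but it does not justify making the question depend on completion.

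**Conclusion.** The concern holds for a defined class of events: those that limit no exercise in the session concerned or the next attended one, those after the last session, and those that end attendance so that no form follows. Among the named sources these depend on being reported at the check-in. Under-recording is possible and its size cannot be computed. It would be wrong to infer that the pilot lacks safety collection, or that its progression decision is compromised.

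The conclusion assumes that the weekly check-in in section 5d is the Monday forum session in section 5c; no other is described. It is confined to the protocol text: parts of section 5c are redacted and the participant information sheet is not in the file, so reporting instructions may exist elsewhere. The Safety entry itself is intact. The change is worth making because it is cheap and concerns a primary outcome, with moderate confidence given those limits.

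**What to change.** In section 5d (Safety), show a short adverse-event question after every session whatever the completion answer, covering the session and the time since the last one. For example: 'During this session or since the last one, have you had any new or worse symptom, any injury, or any unplanned medical contact?'

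Ask the same question at the existing weekly check-in, allowing a private reply because the forum is shared, and at the existing week-7 visit, which covers the time after the last session. State in section 5e that the report will give participants with at least one event over all consented participants, with the number of sessions at which the question was answered.

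The cost is one platform change, one scripted question at the check-in and one at week 7, with no new visit or procedure. At full attendance the post-session question would appear at most 34 × 3 × 6 = 612 times, at a few seconds each. Staff will need some time to classify replies. The recorded count will probably rise and will include background symptoms, with no control arm to separate them; the report should say so.

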Digital prehabilitation for patients undergoing major elective surgery: a single-arm pilot study

IRAS ID: 333460

Study registration: NCT06137781

Study protocol: v2.0 17/01/2024

Study sponsor: Royal United Hospitals Bath NHS Foundation Trust

Research team

Name	Research team role	Professional role	Contact
[name]	Chief Investigator	Consultant in Intensive Care Medicine and Anaesthesia, PreActiv Co-founder	[contact]
[name]	Principal Investigator	Senior Lecturer in Health	[contact]
[name]	Co-Investigator	PreActiv Co-founder	[contact]
[name]	Co-Investigator	Research Lead at PreActiv	[contact]
[name]	Co-Investigator	Tech Lead at PreActiv	[contact]
[name]	Co-Investigator	Physiologist at PreActiv	[contact]
[name]	Co-Investigator	Research Fellow in Exercise Physiology	[contact]
[name]	Co-Investigator	Lecturer in Applied Science	[contact]
[name]	Researcher	Care of the Elderly Registrar	[contact]
[name]	Researcher	Anaesthetic Registrar	[contact]
[name]	Researcher	Postdoctoral Research Associate	[contact]
[name]	Researcher	Preoperative Nurse	[contact]
[name]	Researcher	Preoperative Nurse	[contact]

Protocol summary

Study Title	Digital prehabilitation for patients undergoing major elective surgery: a single-arm pilot study	
Short title	Digital prehabilitation for patients undergoing major elective surgery	
Study Design	Single-centre, single-arm, pilot study	
Study Participants	Patients aged ≥ 50 years that are scheduled for major elective surgery in ≥ 10 weeks	
Planned Sample Size	N = 34	
Intervention Duration	6 weeks	
	Objectives	Outcome Measures
Primary	Assess the feasibility of PreActiv's digital prehabilitation.	Recruitment rate, uptake rate, screen-pass rate, adherence, compliance, retention, safety, acceptability
Secondary	Assess the effect of PreActiv's digital prehabilitation on fitness and wellbeing outcomes in patients awaiting major elective surgery.	
 ● Cardiorespiratory fitness ● Functional fitness ● Resting blood pressure and heart rate ● Self-reported physical activity level ● Quality of life ● Mood ● Economic impact ● Environmental impact
Intervention	Digital prehabilitation including aerobic, resistance, and breathing exercises that are tailored to the patient's mobility and fitness level.	
Dose	3 x 35-minute sessions per week.	

1. Background

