- Acceptability (week 7 only): collected via a survey integrated within PreActiv’s prehabilitation platform containing a combination of Likert scale and open-response questions about participant experiences of using PreActiv’s digital prehabilitation (Appendix 2). Responses to the survey will be fully anonymised, meaning responses cannot be attributed to the participant by name or study ID. Additional feedback will be obtained from comments submitted by participants to the community forum throughout the intervention.

Secondary outcome measurements will be conducted at the University of Bath during week 0 (pre-intervention) and week 7 (post-intervention), with each visit lasting 1-hour:

Participant characteristics

- Baseline characteristics (week 0 only): age, sex, ethnicity, surgery type, comorbidities, medications, mobility, transport to hospital visits (Appendix 3).

Physical assessments

- Resting blood pressure and heart rate will be measured using an automated sphygmomanometer after 15 minutes of seated rest.
- Cardiorespiratory fitness: Cardiopulmonary exercise tests (CPET) will be performed using a ramp-incremental protocol on a cycle ergometer. Body mass, height, and resting blood pressure will be measured prior to commencing exercise. After a 3-minute low-intensity warm-up, participants will be instructed to maintain a consistent cadence of 50-70 rpm during a ramp protocol whereby the resistance against the pedals increases incrementally over time. The rate of the incremental ramp protocol will range from 5-30 watts/minute, based on participant’s ability, with the aim of achieving maximal exertion within 8-12 minutes. Participants will be encouraged to exercise to maximal exertion. Heart rate, blood pressure, oxygen saturation, and rating of

perceived exertion (RPE) rated from 0-10 will be monitored throughout. A 5-minute low intensity cool-down will be completed after the ramp protocol with monitoring of heart rate and blood pressure recovery. Measurements of $VO_{2\text{PEAK}}$ and ventilatory threshold will be derived from CPETs.

- Functional fitness: 1-minute sit-to-stand test (for participants able to transition from seated to standing unsupported) or 1-minute seated push-up test (for participants unable, or requiring support, to transition from seated to standing).

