Appendix 2. Feedback survey

Please tick one box per question that best represents your experience of PreActiv's prehabilitation

1 = Strongly agree, 2 = Agree, 3 = Unsure, 4 = Disagree, 5 = Strongly disagree

	1	2	3	4	5	N/A
Website						
It was easy to register on the website						
The website was user friendly						
I am satisfied with the website						
The website was easy to navigate						
Aesthetically the website looked good						
Exercise prescription						
The exercises in the programme felt appropriate for me						
The exercise videos were easy to follow						
The exercises were challenging						
The rating of perceived exertion scale (0-10) was easy to understand						
It was easy to complete the fitness test in the programme						
I felt motivated to follow the exercise videos						
I enjoyed doing exercises at home						
Booklet/eBook - 'A guide to prehabilitation'						
The booklet contained useful information						
I felt motivated to follow the guidance in the booklet						
I was happy to access the information as an eBook, instead of it being printed						
Support						

The community forum was a good source of support						
I received good tech support with using the platform (if required)						
I received good support from healthcare professionals through the platform						
Overall						
I would recommend the programme to a friend if they were having surgery						
I would continue to use the programme after the research ends						
I feel that the programme helped me to prepare for surgery						
Comments						
Please write any other comments or feedback here:						

The questions detailed above will be asked via PreActiv's website, to allow responses to be fully anonymised. An example screen displaying the questions is shown below:

My PreHub Feedback

Please rate how you found your prehabilitation programme by answering a few quick questions. Your responses are anonymous and will help us improve My PreHub for others.

STEP 1 OF 6

17%

About your experience with My PreHub

	Strongly Agree	Agree	Unsure	Disagree	Strongly Disagree
It was easy to register on the website					
The website was user friendly					
I am satisfied with the website					
The website was easy to navigate					
Aesthetically the website looked good					

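### Acceptability, a primary outcome, rests on one anonymous in-platform survey at week 7 with no described route to participants who disengaged, so the result may over-represent engaged users

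*Combined protocol and SAP*

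**What the plan says.** The Protocol summary lists the primary outcome measures as "Recruitment rate, uptake rate, screen-pass rate, adherence, compliance, retention, safety, acceptability". Section 2 (Aims) defines the last of these as "Acceptability (Likert scale and open-ended survey questions, posts in community forum", so there are two sources.

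- **Survey.** Section 5d (Measurements, Feasibility) gives timing and delivery: "Acceptability (week 7 only): collected via a survey integrated within" the platform. It then states: "Responses to the survey will be fully anonymised, meaning responses cannot be attributed to the participant by name or study ID". Appendix 2 repeats that the questions are put through the website "to allow responses to be fully anonymised". The Appendix 2 items cover the website, the exercises, the booklet, support and an overall view. None asks how many sessions were done.
- **Forum.** Section 5d adds: "Additional feedback will be obtained from comments submitted by participants to the community forum throughout the intervention". Section 5c (Non-exercise intervention) keeps the forum open until one month after surgery and archives the comments for analysis.

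Section 5c (Monitoring of exercise intervention) has researchers email, and then telephone, participants who have lapsed. This is support for adherence and is not listed as acceptability data. Sections 5a and 5e set progression criteria for adherence and retention only.

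**The concern.** A survey that appears once, at the end, inside the platform is most easily met by people still using the platform at the end. Someone who stopped logging in at week 2, or who withdrew, has no described way of reaching it. The plan mentions no exit survey, no invitation sent outside the platform, and no rule on who is asked. Those who disliked the programme may be among those who stop, so their views are the ones most at risk of being missing.

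Full anonymity limits what can be done afterwards. Because "responses cannot be attributed to the participant by name or study ID" and no item records usage, the analyst cannot see whether the responders were mostly high-adherence participants, and cannot compare them with non-responders on adherence, withdrawal or baseline characteristics. Section 5e sets no denominator, response-rate report or bound for the survey.

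At stake is a primary outcome of a pilot whose purpose is to prepare a larger study. A favourable survey figure could be carried into that design without any indication of how many disengaged participants it covers.

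**Working it through.** The plan gives no numerical target for acceptability, so there is no figure of its own to reproduce. The only planned number used is the 34 consented participants (section 5a). That number is consistent with its stated basis: one-sample proportion, 50% against 75%, one-sided alpha 0.05, 90% power. The normal formula gives 30.4, and 34.2 with continuity correction. Nothing below depends on that derivation.

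**Step 1. What the survey can and cannot show**

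| Question | Answerable as planned? |
|---|---|
| How many responded, out of 34 | Yes, by counting responses |
| Whether responders were high or low users | No: no ID and no usage item |
| Whether people who withdrew responded | No |
| Whether responders differ at baseline from non-responders | No |

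**Step 2. Bounds over all 34**

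Let r be the number who respond and a the number of them who agree with an item. Then

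- observed agreement = a / r
- lower bound (all non-responders disagree) = a / 34
- upper bound (all non-responders agree) = (a + 34 − r) / 34
- width = (34 − r) / 34

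The response counts below are assumed, with about 90% of responders agreeing. They are not derived from retention.

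| r | a | Observed | Lower | Upper | Width |
|---|---|---|---|---|---|
| 26 | 23 | 23/26 = 88% | 23/34 = 68% | 31/34 = 91% | 8/34 = 24 points |
| 22 | 20 | 20/22 = 91% | 20/34 = 59% | 32/34 = 94% | 12/34 = 35 points |
| 18 | 16 | 16/18 = 89% | 16/34 = 47% | 32/34 = 94% | 16/34 = 47 points |

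The bounds assume nothing about the views of non-responders. They assume only that each participant answers at most once. With all 34 responding, the width is zero and the concern disappears.

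**Step 3. Do proposed usage bands fit the section 5a zones?**

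The course is 3 sessions × 6 weeks = 18. Then 9/18 = 50% (top of red), 10/18 = 55.6% and 13/18 = 72.2% (both amber), and 14/18 = 77.8% (green). Bands of 0–9, 10–13 and 14–18 therefore match the zones, provided adherence is taken over 18. Section 5d defines it over sessions offered and unlocks each session only after the previous video, so the fixed denominator is an assumption.

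**The case against.** The other side has several good points.

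- **Nobody is excluded.** No text restricts the survey to completers or closes platform access to those who stop, and researchers already contact people who lapse. This stands: calling it a completers-only survey would go beyond the documents. What the plan lacks is a described route to the others.
- **The direction of bias is not shown.** A reader might infer that the result is biased upward. Section 8 names competing preoperative priorities, so some people may stop for reasons unrelated to the programme. This stands: too favourable is the likely direction, not an established one.
- **Some checking is possible.** Responses can be counted against 34, and the lower bound needs no ID. This also stands. What cannot be examined is who responded and how adherent they were.
- **Retention is a different quantity.** A reader might turn the retention zones into a size of bias. Section 3 says "post-intervention testing will be conducted in week 7", the same week as the survey, but section 5d places those measurements in person at the University of Bath, while the survey is online. A participant can do either without the other, so the documents do not support equating survey non-response with loss to follow-up.
- **The forum is a second source.** It runs throughout the intervention and adds information. However, comments are voluntary, sit in the same platform and have no denominator, so it softens the concern without removing it.
- **Anonymity is defensible.** Several investigators hold roles at the platform's company, and anonymity may help candour. This is accepted, and the fix keeps it.

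**Conclusion.** The concern holds in a limited form. As written, the plan risks under-representing disengaged participants in the only structured measure of a primary outcome, and it gives no means of comparing responders by adherence or withdrawal. The survey result is likely, but not certain, to be too favourable.

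The size depends on how many respond, which the documents do not predict. Under the assumed counts, an observed agreement of 88–89% is compatible with as little as 68% (26 responders) or 47% (18 responders) over all 34. These are bounds on what the data could rule out, not estimates of bias.

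The consequence is moderate. Acceptability has no threshold, so the stop/amend/go decision does not change, and disengagement itself is measured by adherence and retention. What is affected is how far the acceptability result can be relied on when the larger study is designed.

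**What to change.** Keep the survey anonymous and make four changes.

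1. Email one common, non-personal link to every consented participant at week 7, or when they stop or withdraw if that is earlier, unless they have declined further contact. State what counts as stopping for this purpose, and ask each person to respond once only. Email contact with participants is already part of section 5c.
2. Add one anonymous item to Appendix 2: sessions done out of the 18 scheduled, in bands 0–9, 10–13 and 14–18. State that the bands correspond to the section 5a zones when adherence is taken over 18.
3. In section 5e, commit to reporting responders out of 34, and results by band where numbers allow, merging small bands to protect anonymity.
4. For each item, report the lower bound that counts non-responders as not endorsing, beside the figure among responders.

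The cost is an email, one survey item and a minor amendment. The headline figure will probably be less favourable. There is also a small loss of anonymity, because with 34 participants a low-use band may hold very few people; merging bands limits this in reports. The responder count and the lower bound need no new data and could be adopted even if the survey itself is left unchanged.
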